### 7.4. MEDICAL HISTORY

Medical history as recorded at screening will be summarized by treatment group using the number and percentage of patients reporting each system organ class (SOC) and preferred term (PT). Medical history will be sorted by descending overall total by SOC and PT using the Medical Dictionary for Regulatory Activities (MedDRA) coding dictionary version 17.1 or later in the summary table.

Medical history listings will be sorted by treatment group, patient number, onset date, end date, SOC, and PT. If the condition is ongoing, the CTCAE grade of the medical condition will also be provided.

### 7.5. OTHER BASELINE CHARACTERISTICS

Cancer diagnosis will be collected as a baseline characteristic. The type of cancer diagnosis (ie, metastatic, locally advanced, or both) will be listed along with the site of the

## Statistical Analysis Plan

local/metastatic disease and whether the cancer represented a recurrence of an earlier cancer.

Prior cancer surgeries will also be listed and include the type and date of the surgical procedure. The listing will be ordered by treatment group, patient, and the date of the surgical procedure.

Smoking history will be listed and will include whether the patient has ever smoked, the patient's current smoking status, and the type and number of tobacco products used. Alcohol history will also be listed and will include the patient's drinking status (drinker/non-drinker) and weekly alcohol consumption.

### 7.6. PRIOR AND CONCOMITANT MEDICATIONS

The summary of medications taken during the course of the study will be presented in tabular form using Anatomical Therapeutic Chemical (ATC) Classification Level 2 and Preferred Term via the World Health Organization Drug classification Dictionary (WHO-DD) version March 2012 or later. All concomitant medications will be summarized by treatment group and sorted by order of decreasing frequency, and by ATC Level 2 Class and PT. Prior medications are medications that started before the start of study treatment in Cycle 1. Concomitant medications are medications that were taken on or after the start of study treatment in Cycle 1, or medication that were started before the start of study treatment dose in Cycle 1 but continued after treatment. That is, medication that started before the start of study treatment dose in Cycle 1 but continued after treatment are considered as both prior and concomitant medication. Concomitant medications will be summarized by treatment group and the ATC Classification Level 2 Term. Prior medications will not be summarized. If a patient has taken a medication more than once, the patient will only be counted once in the total for the summary.

Medications with incomplete end dates will be a concomitant medication if:

- Day and month are missing and the year is equal to or after the year of the first dose date;
- Day is missing and the year is after the year of the first dose;
- Day is missing and the year is equal to the year of the first dose date and the month is equal to or after the month of the first dose date;
- Year is missing; or

## Statistical Analysis Plan

- Date is completely missing.

All medication data will be listed and will include the start date, end date, ATC Classification Level 2, Preferred Term, dose form, dose unit, route of administration and frequency of use. Medications will be flagged as being either prior medications, concomitant medications, or both. Within patients, medications will be ordered by start date, end date, ATC Classification Level 2 and preferred name.

### 7.6.1. Chemotherapy Regimens

Chemotherapy regimens will be summarized and listed separately from other prior and concomitant medications. The classification of the Chemotherapy includes previous, current or post-treatment captured on the *Cancer Therapy* eCRF page.

The number and percentage of patients who had previous, current and post-treatment chemotherapy regimens and disease setting (i.e., metastatic, locally advanced, or other) will be summarized by treatment group. The number of prior chemotherapy regimens administered to patients will be summarized as a categorical variable.

Anticancer therapies will be listed by patient number and treatment group and include the start date, end date, preferred name, disease setting, treatment status, and best response.

### 7.6.2. Radiotherapy Regimens

The number and percentage of patients who had previous, current or post-treatment radiation therapy will be summarized.

Radiation therapies will be listed by patient number and treatment group and include the start date, end date, the type of radiation received, total dose (Gy) and the number of fraction doses.

## Statistical Analysis Plan

### 8. EFFICACY

The following efficacy endpoints will be summarized and analyzed in dose-escalation Part A and dose-expansion Part B:

- Tumour response according to RECIST criteria version 1.1
- Objective response rate (ORR)
- Best overall response rate (BoR)
- Duration of response (DOR)
- Disease control rate (DCR)
- Progression-free survival (PFS)
- Overall survival (OS)

Additionally, survival at 12 months (OS-12) and changes in tumour size will be summarized in Part B.

For dose-escalation Part A, all efficacy data will be summarized by treatment group using descriptive statistics only.

For dose-expansion Part B, all efficacy data will be summarized by treatment group using descriptive statistics and two-sided 80% confidence intervals (CIs) will be provided for the parameter estimates.

No inferential analyses will be conducted to compare the efficacy between treatment groups in either Part A or Part B.

All efficacy data will be analyzed using the Efficacy Set.

#### 8.1. DERIVATION OF RECIST VERSION 1.1 TUMOUR RESPONSES

For all patients, the RECIST tumour response data will be used to determine each patient's tumour response at each visit according to the revised RECIST version 1.1 guidelines (Eisenhauer et al 2009) with modifications to account for the unique response kinetics that have been observed in some patients where responses to immunotherapy may occur after progressive disease (PD) is assessed (Wolchok et al 2009). Specifically, RECIST version 1.1 guidelines have been modified so that PD in the absence of clinical deterioration must

## Statistical Analysis Plan

be confirmed at least 4 weeks after the initial assessment of PD. The modified RECIST guidelines version 1.1 for measurable, non-measurable, target lesions (TLs), non-target lesions (NLTs) and the objective tumour response criteria are presented in Appendix F of the clinical study protocol. These criteria will also be used to determine if and when a patient has progressed in accordance with RECIST and to determine their best objective response.

Baseline radiological tumour assessments are to be performed no more than 28 days before the start of study treatment and should ideally be performed as close as possible to the start of study treatment. Tumour assessments are then performed on Day 15 of Cycle 2 (i.e., at the start of Week 7), at the beginning of each subsequent even-numbered cycle, and at the End of Treatment (EOT) visit. Patients who discontinue treatment for reasons other than PD will continue to undergo tumour assessments every 2 months until PD is noted. To facilitate tumour assessments, a window of  $\pm 3$  days is allowed.

The number and percentage of patients who fell into each of the overall tumour response categories (CR, PR, SD, PD, or NE), into each of the response categories for TLs (CR, PR, SD, PD, or NE), and into the response categories for NLTs (CR, Non-CR/Non PD, PD, NE) will be summarized by treatment group and visit. All tumour response data will be listed.

### **8.2. PRIMARY EFFICACY ENDPOINT AND ANALYSIS**

#### **8.2.1. Dose-escalation and Safety cohorts Part A**

There is no primary efficacy endpoint for dose-escalation Part A.

#### **8.2.2. Dose-expansion Part B - Objective Response Rate (ORR)**

The primary efficacy endpoint for dose-expansion Part B is the objective response rate (ORR). BoR as derived according to Section 8.1 (above) is the primary efficacy variable. Investigator assessed BoR will also be listed.

ORR will be calculated as the percentage of patients in the Efficacy set who have at least one confirmed overall tumour response of CR or PR before any evidence of progression, as defined by RECIST version 1.1. Confirmation of response is made by using 2 consecutive assessments that are at least 4 weeks apart. In the case where a patient has 2 non-consecutive overall visit responses of PR, then, as long as the time between the 2 visits of PR is greater than 4 weeks and there is no PD between the PR visits, the patient will be defined as a responder (PR). Similarly, if a patient has overall visit responses of CR, NE, CR, as long as the time between the 2 visits of CR is greater than 4 weeks, then a best response of CR will be assigned.

## Statistical Analysis Plan

Data obtained up until progression, or the last evaluable assessment in the absence of progression, will be included in the assessment of ORR. Patients who discontinue study treatment without progression, receive a subsequent anti-cancer therapy (note that for this analysis radiotherapy is not considered a subsequent anti-cancer therapy) and then respond will not be included as responders in the ORR. ORR and the corresponding exact 2-sided 80% confidence interval (CI), calculated using the Clopper-Pearson method (Clopper and Pearson 1934), will be summarized by treatment group. The listing summarizing tumour responses by visit (see Section 8.1) will also indicate whether the patient was a responder.

### **8.3. SECONDARY EFFICACY ENDPOINTS AND ANALYSES**

With the exception of ORR, survival at 12 months (OS-12), and change in tumour size the secondary efficacy endpoints are identical for Part A and Part B. ORR is the primary efficacy endpoint for Part B but is a secondary efficacy endpoint for Part A. OS-12 and change in tumour size are not included as secondary efficacy endpoints for Part A.

For both Part A and Part B, efficacy data will be summarized using descriptive statistics. For Part B only, two-sided 80% CIs will be provided for the estimates of all efficacy parameters. No adjustments for multiplicity will be made for any of the secondary efficacy endpoints.

#### **8.3.1. Objective Response Rate**

The analysis of ORR in Part A will be identical to that described for the primary efficacy endpoint in Part B (see Section 8.2.2), with the exception that no CIs for ORR will be provided for Part A.

If there is a sufficient distribution of objective response observed in Part B, the relationship between biomarkers and ORR may be explored using logistic regression.

#### **8.3.2. Best Overall Response**

The patient's best confirmed overall tumour response will be determined using response data from the start of study treatment to the end of study, including any assessments required for confirmation after the EOT. Best overall response will be ordered from best response to worst response as follows: CR, PR, stable disease (SD), or PD, NE (ordered from best to worst). Both CR and PR responses must be confirmed. Patients who achieve CR or PR but for who no confirmation assessment was performed or for who a confirmation assessment was performed but not confirmed will be counted as SD in calculating best overall response. For determination of a best response of SD, the earliest of the dates contributing towards a particular overall visit assessment at least 35 days after study entry will be used. For CR/PR, the initial overall visit assessment that showed a

## Statistical Analysis Plan

response will be used, not the confirmatory scan date. If there are more than one RECIST assessment which contributes to a particular visit, e.g. two different body areas, the later of the two would be used to declare CR/PR.

Best overall response (BOR) will be determined programmatically based on RECIST using all site investigator data up until the first progression event. The denominator will be consistent with that used in the ORR analysis.

For patients whose progression event is death, BOR will be calculated based upon all evaluable RECIST assessments prior to death.

For patients who die with no evaluable RECIST assessments, if the death occurs  $\leq 18$  weeks (i.e., 16 weeks + 2 week to allow for a late assessment within the assessment window) after first dose/administration of study medication, then BOR will be assigned to the progression (PD) category. For patients who die with no evaluable RECIST assessments, if the death occurs  $> 18$  weeks after start of treatment then the patient will be counted as a non-responder and BOR will be assigned to the NE category.

A patient will be classified as a responder if the RECIST criteria for a confirmed CR or PR are satisfied at any time following first dose/administration of study medication, prior to RECIST progression and prior to starting any subsequent cancer therapy.

The number and percentage of patients in each of the overall response categories will be reported by treatment group using the Efficacy Set. The best overall response will be listed for each patient.

For Part A, only descriptive summaries of the best overall response will be provided. For Part B, exact 2-sided 80% CIs will be computed for each response level using the method of Clopper-Pearson (Clopper and Pearson 1934).

The Independent Central Review (ICR) adjudicated results of imaging data will be obtained from Paraxel. The data will be used in the standardization of radiological exams from the Investigator Sites for this trial. The objective will be to assess the concordance rate of BOR at both the sample and patient level for the following:

- Best Independent Central Review (BICR) response results compared to programmatically derived BOR
- BICR response results compared to the investigator assessment of BOR, and
- Investigator assessment of BOR compared to programmatically derived BOR.

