An overall visit response of CR is defined when all TL and NTL lesions present at baseline have disappeared (with the exception of lymph nodes, which must be less than 10 mm to be considered non-pathological) and no new lesions have developed since baseline. An overall visit response of PR is defined when the sum of diameters of the TLs has decreased by 30% or more compared with baseline (with no evidence of progression) and the NTLs are at least stable with no evidence of new lesions. To be assigned a status of PR or CR, changes in tumor measurements must be confirmed by repeat assessments that should be performed no less than 4 weeks after the criteria for response are first met.

SD is defined as neither sufficient shrinkage to qualify for PR nor sufficient increase to qualify for PD. In the case of SD, follow-up measurements must have met the SD criteria at least once after study entry at a minimum interval of not less than 35 days.

When the Investigator is in doubt as to whether PD has occurred and therefore reassesses the patient at a later date, the date of the initial scan should be declared as the date of progression if the repeat scans confirm progression.

Best overall response

A best overall response (CR, PR, SD, PD, or NE ordered from best to worst here) will be determined for each patient based on the best overall visit response recorded from start of study treatment to the EOT, including any assessments for confirmation after the EOT. Confirmation (values of CR or PR in the case of PR and CR for CR is required for best overall response values of CR or PR).

Objective response

A patient is said to have an objective response if he/she has had at least 1 response of confirmed CR or PR before any evidence of progression (as defined by RECIST version 1.1) that is confirmed at least 4 weeks later.

Disease control

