### 8.3.10. Time to First Response

Time to first response is defined as the time (days) from the date of treatment allocation (Part A) or randomization to study drug (Part B) to the date of confirmed CR or PR. This definition will apply regardless of whether the patient withdraws from treatment or receives another anti-cancer therapy prior to response.

The time to first response will be derived based using scan/assessment dates and not visit dates. PFS times will be derived using assessment dates from the "Tumour Assessment" CRF pages.

RECIST assessments/scans contributing towards a particular visit may be performed on different dates. The following rules will be applied:

- Date of response will be determined based on the **earliest** of the dates of the component that triggered progression
- When censoring a patient for time to first response, the patient will be censored at the study day of last evaluable assessment for subjects without response

Time to first response will be analyzed for all evaluable patients using a K-M survival analysis. The number of events, percentiles for the time to first response (25%, 50% (median), and 75% percentiles), and the proportion of patients who responded at 1, 2, 3, and 4 months will be summarized by treatment group. For Part B only, two-sided 80% CIs will be provided for the median PFS times (Brookmeyer and Crowley, 1982), which can be reported using SAS LIFETEST Procedure with CONFTYPE=LINEAR. The 80% CIs for median PFS is the set of all  $t$  which meets  $|ES(t)-0.5|/se(ES(t)) \leq z_{0.9}$ , where  $ES(t)$  is the estimated survival function and  $se(ES(t))$  is the standard error of  $ES(t)$ . Exploratory Analyses

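### Time to first response counts a response that follows another anticancer therapy, ORR excludes it, and the BOR and disease control rules leave its status unclear

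*SAP*

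**What the plan says.** Patients who stop treatment for reasons other than progression are scanned every 2 months until progression (Protocol 4.2.3, SAP 8.1). Neither section stops the scans when a new anticancer therapy starts.

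- **ORR (SAP 8.2.2).** Patients who stop without progression, receive a subsequent anticancer therapy "and then respond will not be included as responders in the ORR". A parenthesis limits this: "note that for this analysis radiotherapy is not considered a subsequent anti-cancer therapy". The section also says "BoR as derived according to Section 8.1 (above) is the primary efficacy variable", but Section 8.1 contains no rule on subsequent therapy.
- **BOR (SAP 8.3.2).** The opening paragraph uses "response data from the start of study treatment to the end of study", including confirmation scans after the end-of-treatment (EOT) visit. A later sentence reads: "Best overall response (BOR) will be determined programmatically based on RECIST using all site investigator data up until the first progression event". Further on, a responder must have a confirmed CR or PR "prior to RECIST progression and prior to starting any subsequent cancer therapy", with no exception for radiotherapy.
- **Time to first response (SAP 8.3.10).** The definition applies "regardless of whether the patient withdraws from treatment or receives another anti-cancer therapy prior to response".
- **Disease control (SAP 8.3.5).** This rests on the Week 12 visit response or, if that is missing or not evaluable, on the next evaluable one. Subsequent therapy is not mentioned.
- **Protocol 8.9.** BOR is "based on the best overall visit response recorded from start of study treatment to the EOT", plus confirmation scans after it. Objective response is limited only by progression, with no bar at subsequent therapy.
- **SAP Section 13.** The only change listed is the exclusion for important protocol deviations in three analysis sets.

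**The concern.** ORR, BOR, time to first response, DOR and disease control are all read from the same scans, and a reader will expect their counts to reconcile. If one endpoint stops at a new therapy and another does not, the number of events in time to first response can exceed the ORR numerator. The surplus consists of responses seen under a different drug.

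The BOR section adds a second difficulty. Two programmers could each follow a sentence in 8.3.2 and classify the same patient differently, although BOR is named as the variable behind the primary endpoint.

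**Working it through.** The plan gives no figure for this issue, so the check is to apply each rule to two patients and then scale the result.

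**Patient X** stops without progression, starts a new systemic anticancer therapy, and then has a first PR on follow-up scans, confirmed, with no progression. **Patient Y** is the same, except that the intervening treatment is radiotherapy.

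| Rule | Patient X | Patient Y |
|---|---|---|
| ORR, SAP 8.2.2 | not a responder | responder |
| BOR data window, SAP 8.3.2 | PR | PR |
| Responder sentence, SAP 8.3.2 | not a responder | not a responder, on its plain wording |
| Time to first response, SAP 8.3.10 | event | event |
| DOR and durable response, SAP 8.3.3 and 8.3.4 | no therapy rule; enters as a confirmed response | same |
| Disease control, SAP 8.3.5, if a scan under the new treatment supplies the Week 12 result | yes, by default | yes, by default |
| Objective response, Protocol 8.9 | responder, on its plain wording | responder, on its plain wording |
| BOR, Protocol 8.9, if the response is first seen after EOT | not PR | not PR |

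The rows lead to four observations.

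1. For X, 8.2.2 and 8.3.10 conflict in express words. With k patients like X in an arm, time to first response has k more events than the ORR numerator.
2. For X, two sentences of 8.3.2 conflict, and the SAP names no BOR category for a patient whose response is barred.
3. For Y, ORR counts the response and the 8.3.2 responder sentence does not. This mismatch runs in the opposite direction.
4. The bar on X in ORR, and the BOR window to end of study, both differ from Protocol 8.9. Neither is listed in Section 13.

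**Scale.** The difference in a rate is 100 × k/n points. The documents give no value for k, so k = 1 is used for illustration.

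- n = 48 (B7 or B8): 1/48 = 2.1 points.
- n = 35 (maximum for B3, and for B4 as originally sized): 1/35 = 2.9 points.
- n = 12 (B5 or B6): 1/12 = 8.3 points.

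The SAP's exact 80% Clopper-Pearson interval has as its lower limit the 10% quantile of Beta(x, n − x + 1) and as its upper limit the 90% quantile of Beta(x + 1, n − x). When x = 0 the lower limit is 0.

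- 12/48 = 25.0% (16.9 to 34.8); 13/48 = 27.1% (18.7 to 37.0).
- 7/35 = 20.0% (11.5 to 31.3); 8/35 = 22.9% (13.8 to 34.5).
- 0/12 = 0% (0 to 17.5); 1/12 = 8.3% (0.9 to 28.7).

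**The case against.** The strongest reply is that the primary endpoint is already protected. ORR excludes these responses, efficacy is descriptive, and no between-group inference is planned (SAP Section 8). Time to first response is absent from the protocol's secondary outcome measures, from SAP 4.2.2 and from the endpoint list that opens Section 8. Its text still refers to progression and to median PFS, which suggests that the clause was carried over from the PFS section. This limits the consequence, but the clause is explicit and would be programmed as written.

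Three stronger readings are tempting, and the documents do not support them.

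- **That BOR plainly credits the next drug's response.** The responder sentence in 8.3.2 requires CR or PR before any subsequent cancer therapy, and 8.2.2 links BOR to ORR, so a single responder rule is the natural intention. The reference in 8.3.2 to confirmation scans after EOT would be redundant if the window really ran to end of study, which points to loose wording. What stands is an internal conflict and an unnamed category.
- **That disease control is defined to include such patients.** The text is silent. The route is also narrow: stopping without progression, starting a new therapy, and having a non-progression scan, all by about Week 12 or by the next evaluable scan if Week 12 is missing or not evaluable. This is a gap that counts patients by default.
- **That the comparison of central, investigator and programmed BOR uses different scan windows.** No document states the window for the central read or for the investigator's BOR.

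A reader might also estimate the size from the response rates in Protocol 1.1.5, 36% with cetuximab plus chemotherapy and 20% with chemotherapy. Those are first-line results. The documents give no response rate after AZD9150 plus MEDI4736 and no count of patients who would follow this path. The response would also have to precede progression and be confirmed at least 4 weeks later. No such estimate is used here.

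**Conclusion.** The point holds in a limited form. There is one express contradiction, between 8.3.10 and 8.2.2. There is one internal conflict in 8.3.2, between the data window and the responder sentence, and the radiotherapy definition differs between 8.2.2 and 8.3.2. Disease control has no rule. The SAP's bar on ORR and its BOR window wording also differ from Protocol 8.9 without being listed as changes.

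The number of affected patients is unknown and may be zero. Each one moves a rate by 2.1 points in a 48-patient arm and 8.3 points in a 12-patient arm. The conclusion assumes only that follow-up scans continue after a new therapy starts, which the schedule permits. It does not affect the primary ORR as defined in 8.2.2.

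**What to change.** 1. **SAP 8.3.10:** delete the clause about receiving another anticancer therapy before response, and restrict events to patients who are responders under 8.2.2. All others are censored by the rule already in that section.
2. **SAP 8.3.2:** state that a BOR of CR or PR follows the same subsequent-therapy rule and the same radiotherapy definition as 8.2.2, and name the category that a barred patient receives.
3. **SAP 8.3.5:** treat a Week 12 assessment made after the start of a subsequent systemic anticancer therapy as no disease control. Apply this also to a later scan that stands in for a missing or non-evaluable Week 12 result.
4. **SAP 8.3.3 and 8.3.4:** restrict DOR and durable response to ORR responders, but keep their end and censoring dates tied to PFS as written. PFS runs regardless of other therapy, and 8.3.3 requires the end of response to coincide with the PFS date, so cutting DOR at new therapy would break that link.
5. **SAP Section 13:** list the subsequent-therapy bar on ORR and the BOR window wording as differences from Protocol 8.9.

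Do not add a requirement that confirmation precede the new therapy. Section 8.2.2 bars patients who receive therapy and then respond, so that addition would change the primary endpoint for a patient whose response was first seen before the new therapy and confirmed after it.

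The cost is SAP wording and one derived date from the Cancer Therapy eCRF page described in SAP 7.6.1. BOR, disease control and time to first response may become slightly less favourable.
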